3.1.6. PRIOR THERAPY

- Patients must have fully recovered from the acute toxic effects of all prior chemotherapy, immunotherapy, or radiotherapy prior to entering on this study.

- No limitation on the number of prior chemotherapy regimens that the patient may have received prior to study entry.
- Myelosuppressive chemotherapy: The last dose of all myelosuppressive anticancer drugs must be at least 3 weeks prior to study entry.
- Immunotherapy: The last dose of immunotherapy (monoclonal antibody or vaccine) must be at least 4 weeks prior to study entry.
- Biologic (anti-cancer agent): The last dose of all biologic agents for the treatment of the patient's cancer (such as retinoids or tyrosine kinase inhibitors) must be at least 7 days prior to study entry.
- Radiation therapy: The last dose of radiation to more than 25% of marrow containing bones (pelvis, spine, skull) must be at least 4 weeks prior to study entry. The last dose of all other local palliative (limited port) radiation must be at least 2 weeks prior to study entry.
- Stem Cell Transplantation. At least 2 months post-autologous stem cell transplant or at least 3 months post-allogeneic transplant and recovered from toxicities without evidence of graft versus host disease and on stable doses of immunosuppressive medications if required.
- Growth Factors. The last dose of colony stimulating factors, such as filgrastim, sargramostim, and erythropoietin, must be at least 1 week prior to study entry, the last dose of long-acting colony stimulating factors, such as pegfilgrastim, must be at least 2 weeks prior to study entry.

3.1.7. CONCURRENT THERAPIES: No other anti-cancer therapy (chemotherapy, biological therapy, radiation therapy) is permitted.

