#### **2.1.2. Neurofibromatosis Type 1 and MPNST**

Approximately half of all MPNST arise from individuals with Neurofibromatosis Type 1 (NF1) [6]. NF1 is a common autosomal dominant tumor predisposition syndrome. The NF1 gene encodes for a protein called neurofibromin, which

includes a GTPase activating protein that regulates hydrolysis of Ras-GTP to Ras-GDP [7, 8]. Patients with NF1 have dysfunctional or decreased levels of neurofibromin, which contributes to dysregulated Ras and tumorigenesis [9]. MPNSTs are the most common NF1 associated malignancy. The lifetime risk of MPNST in NF1 is 8-13% compared to 0.001% in the general population [6, 10]. The majority of NF1-associated MPNST arise from pre-existing plexiform neurofibromas [11], which may lead to delay in diagnosing MPNST in patients with NF1 because the clinical indicators of malignancy such as mass and pain may also be features of benign plexiform neurofibromas. NF1-associated MPNST in comparison to sporadic are more frequently located in the trunk, tend to be large (>5cm) [12] and may have greater propensity to metastasize [10]. These may be potential reasons why NF1-associated MPNST appear to have worse outcome than sporadic MPNST [13, 14]. Gene expression profiling of NF1 associated and sporadic MPNST did not identify molecular signatures that could reliably distinguish between both groups [15, 16].

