- 3.2.8. Hypersensitivity to active or inactive excipients of rapamycins (sirolimus, temsirolimus or everolimus) or selumetinib or drugs with similar chemical structures or class to sirolimus or selumetinib.
- 3.2.9. Patients unwilling or unable to comply with the protocol.

- 3.2.10. Seville orange, star fruit, grapefruit and their juices, and St. John's Wort use are not allowed while on study.
- 3.2.11. Exposure to strong or moderate inhibitors or inducers of CYP3A4/5, Pgp (MDR1) and BCRP if taken within the stated washout periods before the first dose of study treatment (Appendix II).
- 3.2.12. Exposure to specific substrates of drug transporters OATP1B1, OATP1B3, MATE1 and MATE2K within the appropriate washout periods (a minimum of 5 x reported elimination half-life) before the first dose of study treatment (Appendix II)

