## 4. REGISTRATION PROCEDURES

### 4.1. General Guidelines

After obtaining Informed Consent, eligible patients will be enrolled on this trial. Subjects will be registered by local sites through an electronic database, and will be issued a subject unique identifying numbers for eligible participants. An investigator is required to prepare and maintain adequate and accurate case histories designed to record all observations and other data pertinent to the investigation on each subject treated with the investigational product in the study or registered to the study. SARC may request faxed copies of selected source documents with PHI redacted for verification of records, accuracy of electronic submissions and review of data.

While all study evaluations must be performed by the Investigator as described in Section 10, Study Evaluations and Study Calendar, only data related to the primary and secondary endpoints, as well as safety data, will be captured in the eCRFs.

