## 10. STUDY EVALUATIONS AND STUDY CALENDAR

### 10.1. SCREENING STUDIES

The following procedures will be performed within **4 weeks** prior to start of enrollment unless otherwise stated:

- Informed consent
- Review concomitant medications
- FDG-PET
- Baseline radiologic imaging: Evaluation of other measurable or evaluable disease sites by appropriate radiological evaluation (i.e. CT scan, MRI)

The following procedures will be performed within **14 days** prior to start of enrollment unless otherwise stated:

- Serum Pharmacodynamic and Immune Markers: Mandatory blood samples for pharmacodynamics, genomics and immune infiltrates
- Tumor biopsy: Optional serum/tissue samples for pharmacodynamics, genomics and immune infiltrates
- History/demographics
- Physical exam: vital sign, height, weight, body surface area
- Performance status: Lansky/Karnofsky (Appendix I)
- Hematology: complete blood count (CBC), differential
- Serum Chemistry: ALT, AST, alkaline phosphatase, bilirubin, BUN, creatinine, electrolytes, calcium, magnesium, phosphorus, total protein, albumin, serum creatinine phosphokinase.
- Fasting\* glucose and Fasting serum lipid profile (triglycerides, total cholesterol, HDL and LDL) \*Fasting = 12 hours prior to glucose testing and lipid testing
- Echocardiogram or Cardiac MRI and ECG (performed within 4 weeks prior to start of enrollment)
- Ophthalmology evaluation: A complete ophthalmology evaluation will be performed pre-treatment. Particular emphasis will be given to the evaluation of corneal opacifications and retinal changes.
- Patient reported pain severity and pain interference assessments.

The following procedures will be performed within **7 days** prior to start of therapy unless otherwise stated:

- Serum or urine pregnancy: required for females of childbearing potential.

NOTE: Eligibility labs/evaluations performed can be counted as pre-treatment evaluations as performed in time frame requested.

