### **13.4. Analysis of Secondary Endpoints**

Summary statistics will be used to describe the study population and baseline characteristics.

Progression free survival will be determined using the Kaplan-Meier method, with PFS at important time points (6 or 12 months for example) reported along with 95% two sided confidence intervals.

Toxicities to be summarized descriptively and tabulations on the type, severity, and relationship to study treatment will be performed.

Changes in FDG-PET avidity, tumor biomarkers, pain severity and pain interference ratings, and immune markers will be exploratory and summarized using descriptive statistics and when feasible compared using Wilcoxon rank test or pairwise t-test. Correlations to imaging response, toxicity, and immune markers will be made if feasible.

The comprehensive genomic analyses including next generation sequencing and ctDNA analysis will be performed in the Oncogenomics laboratory ([name]/NCI). Bioinformatics analysis will be primarily performed at the NCI using well-established pipelines previously developed.

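### Baseline pharmacodynamic samples and FDG-PET can be taken while a patient is still on an earlier MEK or mTOR inhibitor, and the plan does not separate such patients (low severity, cheap to fix)

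*Combined protocol and SAP*

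**What the plan says.** **Eligibility.** Section 3.1.6 covers "The last dose of all biologic agents for the treatment of the patient's cancer" and requires that the last dose of these agents, "such as retinoids or tyrosine kinase inhibitors) must be at least 7 days prior to study entry". MEK and mTOR inhibitors are not named; I read them as falling under this rule when given for the cancer. On chemotherapy the same section states "No limitation on the number of prior chemotherapy regimens that the patient may have received prior to study entry". In section 3.2 the only criterion that names the study drug classes is 3.2.8: "Hypersensitivity to active or inactive excipients of rapamycins (sirolimus, temsirolimus or everolimus) or selumetinib". Sections 3.2.1 and 3.2.3 bar patients who are currently receiving other anti-cancer agents or chronic immunosuppressants, not patients who received them earlier.

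**Baseline sampling.** Section 10.1 lists, among procedures due within 14 days before enrolment, "Serum Pharmacodynamic and Immune Markers: Mandatory blood samples for pharmacodynamics, genomics and immune infiltrates", and the optional tumour biopsy with it. Baseline FDG-PET is in the 4-week list. Section 3.1 allows treatment to start up to 7 days after enrolment.

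**Use of the baseline.** Section 1.3 compares pERK, pS6, pAKT and GLUT1 before and after treatment, and explores early FDG-PET change. Section 2.5.2 assigns pS6 and pAKT to mTOR inhibition and pERK to MEK inhibition.

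**Recording and analysis.** Section 4.1 says "only data related to the primary and secondary endpoints, as well as safety data, will be captured in the eCRFs". Section 13.4 says "Summary statistics will be used to describe the study population and baseline characteristics" and does not list prior targeted therapy. Sections 13.1 and 13.3 put all evaluable patients into one clinical benefit rate.

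**The concern.** A pre/post comparison of target inhibition needs an untreated baseline. If pERK is already low because a patient is still on a MEK inhibitor, or pS6 because of an mTOR inhibitor, the change on study is too small and real target inhibition can look absent.

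Exposure is plausible from the protocol's own background. Table 1 lists two mTOR-inhibitor combination trials in refractory MPNST (25 and 20 patients). Section 2.2.1 describes selumetinib in NF1 plexiform neurofibroma. Section 2.1.2 adds "The majority of NF1-associated MPNST arise from pre-existing plexiform neurofibromas", and section 3.3 expects about half of the patients to have NF1. A MEK inhibitor taken for a benign plexiform neurofibroma is not clearly covered by a washout worded for treatment of the cancer.

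The second, smaller issue is interpretation. With at most 21 patients and a first-stage decision on 7, a reader of the results will want to know who had already received one of the two drug classes. The plan does not say that this will be reported.

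**Working it through.** **1. Timing.** Let day 0 be enrolment, taken as the same as study entry.

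| Item | Source | Window |
|---|---|---|
| Latest permitted last dose of the earlier agent | 3.1.6 | day −7 |
| Baseline pharmacodynamic blood, optional biopsy | 10.1 | day −14 to day 0 |
| Baseline FDG-PET | 3.1, 10.1 | day −28 to day 0 |

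A patient who stops on day −7 can be sampled on drug for the first 7 of the 14 days, and scanned on drug for the first 21 of the 28 days.

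**2. Is the washout itself too short?** Fraction left = 0.5^(hours since last dose / half-life). Half-lives are from section 2.2: sirolimus 13 h (day 1) and 24 h (day 28), selumetinib 5 to 7 h. The longer value of each is used.

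| Time since last dose | Sirolimus, 24 h | Selumetinib, 7 h |
|---|---|---|
| 24 h (sample on day −6) | 0.5^1 = 50% | 0.5^3.43 = 9.3% |
| 72 h (sample on day −4) | 0.5^3 = 12.5% | 0.5^10.3 = 0.08% |
| 168 h (day 0) | 0.5^7 = 0.8% | 0.5^24 = 0.000006% |

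By entry both study drugs are almost fully cleared. The problem is when the sample is taken, not the length of the washout. These half-lives do not cover other MEK or mTOR inhibitors, and drug level is not the same as marker recovery.

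**3. The stated design.** Rule from section 13.1 and the Synopsis (section 13.2 prints the cut-offs with a strict inequality; that reading is not used): stop if 0 of 7 benefit, otherwise continue to 21 and declare activity at 3 or more.

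- Early stopping at 5%: 0.95^7 = 0.698. The plan says 69.8%.
- Expected size at 5%: 7 + 14 × (1 − 0.698) = 11.2. The plan says 11.2.
- Probability of declaring activity = P(at least 3 of 21) − P(0 of 7) × P(at least 3 of 14). At 30%: 0.9729 − 0.0824 × 0.8392 = 0.904. The plan says 90%.
- The same formula at 5% gives a type I error of 0.064, within the stated 0.10.

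The plan's figures reproduce.

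**4. Illustration of dilution.** The documents give neither the exposed share f nor the benefit rate q in exposed patients; both are assumptions. Overall rate = (1 − f) × 0.30 + f × q, with the rule unchanged.

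| Power | q = 0% | q = 5% | q = 10% | q = 15% |
|---|---|---|---|---|
| f = 0 | 90.4% | 90.4% | 90.4% | 90.4% |
| f = 10% | 86.4% | 87.2% | 87.9% | 88.6% |
| f = 20% | 80.9% | 83.0% | 84.8% | 86.4% |
| f = 30% | 73.5% | 77.5% | 80.9% | 83.9% |

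Example: f = 20% and q = 5% give 0.8 × 0.30 + 0.2 × 0.05 = 0.25, and power 83.0%. The chance of stopping at stage 1 is then 0.75^7 = 13.3%, against 0.70^7 = 8.2% with nobody exposed.

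**5. Direction.** If unexposed patients have the null rate of 5% and exposed patients 0%, type I error falls from 0.064 to 0.037 at f = 20%. Exposure can hide activity. It does not create a false positive.

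**The case against.** **Frequency.** No passage counts exposed patients. The two mTOR trials in Table 1 treated 45 patients together, in a disease that section 2.1.3 describes as progressing in under 2 months at the median. Selumetinib is described as still in development. A reader might infer that exposure is likely; the documents support only that it is possible. This stands.

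**Resistance.** A reader might infer that a tumour which failed one class is resistant to the combination. Section 2.1.4 points the other way: in the mouse model, GLUT1 suppression before regression needed both pathways blocked, and mTORC1 inhibition alone was cytostatic. Exposure is also not progression, since a drug may have been given for a plexiform neurofibroma or stopped for another reason. This stands. It also weakens the GLUT1 and PET part after exposure to one class; pERK, pS6 and pAKT remain directly open to it.

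**Population.** Section 13.1 sets the 30% target for the patients enrolled, not for unexposed patients. An unselected refractory population is a legitimate choice. Accrual of 1 to 2 patients per quarter over about 30 months gives 10 to 20 patients, so excluding single-class exposure would be a real cost. This stands.

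**Records.** Sites must know the drug and the last-dose date to apply the washout, and a history is taken. The case report forms and the operations manual are not among the documents, so it cannot be said that the information goes uncollected. What can be said is that the protocol states no plan to capture or report it.

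**Weight.** The marker comparisons are exploratory and descriptive. That limits the severity. It does not remove the timing gap, which follows directly from the two windows.

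**Conclusion.** The point holds in a narrow form, as a cheap improvement of low severity. The 14-day blood and biopsy window and the 4-week PET window both open before an earlier MEK or mTOR inhibitor has to be stopped, so a sample labelled pre-treatment can be a treated one. This follows from sections 3.1.6 and 10.1 without any assumption, apart from reading study entry as enrolment and these inhibitors as covered by the washout.

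The effect on the primary endpoint cannot be sized from the documents. The range of 88.6% to 73.5% against 90.4% rests on assumed exposure of 10% to 30% (about 2 to 6 of 21 patients) and assumed benefit of 0% to 15% in them. It shows direction and scale only.

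Three stronger readings should be resisted. The documents do not show that the washout is too short for the study drugs. They do not justify excluding everyone with single-class exposure. And they do not make a negative result uninterpretable: at 20% exposure, power stays above 80% even with no benefit in those patients.

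**What to change.** 1. In section 10.1 and the study calendar, require that for any patient coming off a MEK or mTOR inhibitor, including one given for a plexiform neurofibroma, the baseline pharmacodynamic blood (and the biopsy, if taken) is collected after the interval in section 3.1.6 has passed. Do the same for baseline FDG-PET where feasible. A patient who stops on day −7 reaches that point only on day 0, so the window should be allowed to run to the first dose, which section 3.1 permits up to 7 days after enrolment.
2. State in section 3.1.6 whether the interval applies to such a drug when it was not given for the cancer.
3. At registration, record drug class, best response and date of last dose.
4. In section 13.4, add a descriptive table of the clinical benefit rate with and without exposed patients, with no test.

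Excluding patients already treated with a MEK and an mTOR inhibitor together is optional. The two selumetinib plus temsirolimus studies in section 2.2.3 included no MPNST patients, so few may be affected.

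Cost: a narrower sampling window for a few patients, three registration fields, and one small table that will be imprecise. Items 1, 3 and 4 remove nobody from eligibility.

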#### 3.1.8. PERFORMANCE STATUS

- Lansky/Karnofsky performance level  $\geq 50\%$  (See Appendix I).
- Patients who are unable to walk because of paralysis or motor weakness, but who are up in a wheelchair will be considered ambulatory for the purpose of calculating the performance score.

#### 3.1.9. HEMATOLOGIC FUNCTION

- Peripheral absolute neutrophil count (ANC) of  $\geq 1000/\mu\text{L}$
- Platelet count  $\geq 75,000/\mu\text{L}$  (transfusion independent (no transfusion within at least 7 days prior to enrollment))

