### 3. PATIENT SELECTION

#### 3.1. Eligibility Criteria

Patients must have baseline evaluation performed prior to the first dose of study drugs and must meet all inclusion/exclusion criteria. Results of all baseline evaluations, which assure that all inclusion/exclusion criteria have been satisfied must be reviewed by the Principal Investigator or his/her designee prior to enrollment of the patient. In addition, the patient must be thoroughly informed about all aspects of the study, including study visit schedule and required evaluations and all regulatory requirements for informed consent. The written informed consent must be obtained from the patient prior to enrollment. The following criteria apply to all patients enrolled onto the study unless otherwise specified.

All clinical and laboratory studies must be performed within 14 days prior to enrollment unless otherwise indicated. Imaging studies for baseline scans must be obtained within 4 weeks prior to enrollment. Patients must start therapy no later than 7 calendar days after the date of study enrollment.

**INFORMED CONSENT:** All patients or guardians must sign a document of informed consent indicating their understanding of the investigational nature and the risks of this study before any protocol related studies are performed. Patients under 18 years of age will sign an assent document prior to treatment.

**DURABLE POWER OF ATTORNEY (DPA):** Patients will be offered the opportunity to assign a DPA so that another person can make decisions about their medical care if they become incapacitated or cognitively impaired.

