### 5.2. Criteria to start subsequent cycles

(Refer to section 6 for dose modifications)

A cycle may be repeated every 28 days if the patient has at least stable disease, has again met the ANC, platelet, hepatic, and renal function defined in Section 3.1, and has not met one of the off protocol therapy or off study criteria in Section 5.6 and 5.8. Up to 21 days (to day 49) will be allowed between cycles for recovery without modifying drugs on subsequent cycles if toxicity did not meet criteria requiring dose modification.

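### The transfusion-free and growth-factor-free intervals are not tied to the blood count that qualifies the patient, so a supported count can meet eligibility (minor, cheap to correct)

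*Combined protocol and SAP*

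**What the plan says.** **Timing of the count.** Section 3.1: "All clinical and laboratory studies must be performed within 14 days prior to enrollment unless otherwise indicated". Section 10.1 lists "Hematology: complete blood count (CBC), differential" in its 14-day block and sets no tighter window. It also lets eligibility tests serve as the pre-treatment tests. Under Section 3.1, treatment must begin within 7 calendar days of enrolment.

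**Platelets.** Section 3.1.9 sets a limit of 75,000/µL and requires the patient to be "transfusion independent (no transfusion within at least 7 days prior to enrollment"). The clock runs back from enrolment.

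**Neutrophils.** The same section sets "Peripheral absolute neutrophil count (ANC) of" at least 1000/µL and says nothing about growth-factor support. Support is handled separately in Section 3.1.6: "The last dose of colony stimulating factors, such as filgrastim, sargramostim, and erythropoietin, must be at least 1 week prior to study entry". Long-acting agents, "such as pegfilgrastim, must be at least 2 weeks prior to study entry". Study entry is not defined.

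**Recheck.** Section 5.2 lets a cycle be repeated if the patient "has again met the ANC, platelet, hepatic, and renal function defined in Section 3.1". This governs repeat cycles only. Section 10.2 and the Study Calendar ask for weekly blood counts in cycle 1. They name no day 1 draw and no count that must be met before dosing.

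**The concern.** A support-free interval shows that a count is the patient's own only if the interval precedes the count. Here the interval precedes enrolment (or study entry), while the count may precede the interval. A patient transfused and counted on day -10, then enrolled on day 0 with no further transfusion, meets the platelet criterion on a count that says nothing about transfusion independence.

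Two things are at stake. First, the platelet criterion may not test what it states. Second, toxicity is a secondary objective (Section 1.2), and Section 13.4 tabulates it by relationship to treatment. Section 2.2.3 reports neutropenia as dose limiting with selumetinib plus temsirolimus, and Section 7.3.2 lists thrombocytopenia in 30 of 100 patients on sirolimus. Early cytopenias are therefore expected. If the baseline count was supported, a fall in cycle 1 may be loss of support, drug effect or both. The first protocol-defined check against the limits comes at cycle 2.

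**Working it through.** The plan gives no figure to reproduce here; the check is day arithmetic.

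**Inputs** (enrolment = day 0)
- Qualifying count on day c, from -14 to 0: 15 permitted days (Sections 3.1 and 10.1).
- Washout w: 7 days for transfusion (3.1.9), 7 days for short-acting growth factor and 14 days for long-acting (3.1.6).
- First dose on day 0 to +7 (3.1).
- Assumptions: study entry means enrolment, and support given exactly w days before is permitted.

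**Formula.** Support may be given on any day up to -w. The shortest permitted gap between support and count is g(c) = max(0, c + w).

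| Count drawn on | w = 7 (transfusion, short-acting) | w = 14 (long-acting) |
|---|---|---|
| day -14 | 0 | 0 |
| day -10 | 0 | 4 |
| day -7 | 0 | 7 |
| day -6 | 1 | 8 |
| day -1 | 6 | 13 |
| day 0 | 7 | 14 |

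**Results**
- For transfusion and short-acting growth factor the gap can be zero on days -14 to -7, which is 8 of the 15 permitted days. For long-acting growth factor it can be zero only on day -14.
- In all three cases the gap can be shorter than the plan's own washout on days -14 to -1 (14 of 15 days). Only a count on day 0 guarantees the full interval.
- These are counts of permitted days, not proportions of patients.
- Maximum age of the qualifying count at first dose: 14 + 7 = 21 days.

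**Sensitivity to the assumptions**
- If a transfusion on day -7 is itself barred, the zero-gap days for platelets become -14 to -8. The conclusion moves by one day.
- If study entry means first dose on day d, then g(c) = max(0, c + w - d). With d = 7 and w = 7 this is max(0, c), so the gap can be zero on all 15 days. With d = 7 and w = 14 it is max(0, c + 7), so the long-acting case becomes the w = 7 column. The other reading of the undefined term makes the mismatch larger.

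**With the count required to follow the interval.** The shortest gap becomes 7, 7 and 14 days whatever the draw date. The maximum age at first dose stays 21 days, because that depends on whether counts are confirmed before dosing.

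**The case against.** The best reply is that nothing here contradicts itself. Section 3.1.9 says expressly what it means by transfusion independence and picks enrolment as the reference date. Section 3.1 separately sets a 14-day laboratory window. Choosing another reference date is a preference. There are also safeguards: Section 3.1.6 requires full recovery from the acute toxic effects of prior therapy, Section 3.1 has baseline results reviewed before enrolment, a patient transfused on day -10 must still go 7 days without another transfusion, and weekly cycle 1 counts would reveal a low value early.

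Much of this stands. The text is coherent, so this is an improvement and not an error. The safeguards narrow the scenario, but none sets a count or a date for it, so they do not close the gap.

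Stronger readings are tempting but not supported:
- *That the neutrophil criterion demands an unsupported count.* It does not say so. The transfusion condition likewise attaches to platelets only.
- *That low starting counts cause holds and so lower the clinical benefit rate.* Section 6.2 lists Grade 4 thrombocytopenia, or hematological toxicity interrupting treatment for more than 21 days. Neutropenia by itself is not a listed trigger. Section 5.2 allows up to 21 days for recovery between cycles without dose change, and a delayed cycle is not a lost one. Failure to meet restart parameters can end protocol therapy (Section 5.5), but nothing shows that supported baselines would produce it.
- *That a trial decision could change.* The stopping rule in Section 13.5 counts only non-hematologic events, and toxicity is otherwise descriptive.
- *That a 21-day-old count uses up the whole 3-week chemotherapy gap.* These are different clocks. The 3 weeks run to study entry. With entry read as enrolment, a first dose on day +7 is at least 21 + 7 = 28 days after chemotherapy.

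**Conclusion.** The point holds as a minor one. As written, the qualifying platelet count can follow a transfusion with no interval on days -14 to -7, and the qualifying neutrophil count can be drawn during filgrastim on those days or on the day of pegfilgrastim at day -14. The count can be 21 days old at first dose, with no stated confirmation before then. The consequences are limited to a platelet criterion that may not show transfusion independence and a possibly supported baseline for judging early cytopenias.

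This rests on reading study entry as enrolment and on support exactly 7 or 14 days before being permitted; the other readings shift the boundary by a day or widen the mismatch. How many patients would be affected is unknown, and no effect on the primary endpoint is shown.

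**What to change.** 1. Define study entry in Section 3.1.6.
2. State in Sections 3.1.6 and 3.1.9 that the qualifying neutrophil and platelet counts must be drawn after the existing support-free interval has elapsed, with no transfusion or growth factor between that count and enrolment. Keep the enrolment anchor as well: running the interval from the count alone would allow support between count and enrolment. Limits and interval lengths stay as they are.
3. Reconcile Sections 3.1, 5.2, 10.1 and 10.2 on whether the Section 3.1 counts must be confirmed before the first dose. That is for the sponsor to settle; item 2 alone leaves the 21-day maximum age unchanged.

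**Cost.** Eligibility wording, and an occasional repeat blood count or short enrolment delay. If a site relies on a day -14 count, the patient would in effect need 14 + 7 = 21 days free of transfusion or short-acting growth factor before enrolment, or 14 + 14 = 28 days free of long-acting growth factor. Repeating the count close to enrolment avoids most of that.
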